### 4.3 Radiotherapy

Locally-advanced NSCLC is typically treated with thoracic radiotherapy, often in combination with concurrent chemotherapy. Despite advances in the evaluation, treatment techniques, and supportive care measures provided to locally advanced NSCLC patients, local disease progression and distant metastases frequently develop following definitive therapy. Randomized trials have tested changes or additions to systemic therapy[14-18], radiotherapy dose escalation, and the addition of surgical resection[19] but have failed to improve overall survival for this patient population. A recent landmark randomized trial demonstrated that radiotherapy dose escalation, applied to the primary tumor and all involved regional lymph nodes, may reduce survival rates, highlighting gaps in our understanding of the effects of thoracic radiotherapy for LA-NSCLC.

[figure not shown]
A growing body of literature indicates that minimizing cardiac irradiation should be a goal in planning thoracic radiotherapy. Recent publications have demonstrated a strong association between cardiac irradiation and both cardiac events [20-23] and all-cause mortality[17]. The risks of cardiac irradiation may be highest in subjects with comorbid conditions such as existing heart disease[20, 21] or a smoking history [23], which are common in NSCLC patients. Somewhat surprisingly, these effects have been seen within a few years of radiotherapy delivery [17, 20-22] and in populations with high risk of cancer-specific mortality [17, 20, 21]. In retrospect, this is consistent with previous analyses demonstrating that excessive [24] or unnecessary [25] mediastinal irradiation for lung cancer can meaningfully reduce survival rates. Thoracic irradiation may directly lead to coronary artery stenosis[26] and may also impair patients' immune systems [27].

Based on accumulating evidence demonstrating the prognostic and predictive value of FDG-PET metrics [28-32], we recently performed a single-institution phase II study testing dose-painted intensity-modulated radiotherapy (IMRT) as a strategy to improve the efficacy and safety of chemoradiotherapy for locally advanced NSCLC[33]. In that trial, tumors and lymph nodes deemed to be at low risk for local progression following chemoradiotherapy were treated with a relatively low radiotherapy dose of 52.5 Gy. Our results indicate that this novel strategy yields high rates of metabolic response, local disease control, and overall survival. The aforementioned high-profile studies highlighting the importance of minimizing cardiac irradiation in NSCLC

patients will draw additional attention to our dose-painting approach for locally advanced NSCLC.

Kaplan-Meier curves for overall survival and progression-free survival from the Montefiore/Einstein phase II study of dose-painted IMRT for LA-NSCLC.

Cumulative incidence curves for disease progression in individual tumors or lymph nodes from the Montefiore/Einstein phase II study of dose-painted IMRT for LA-NSCLC. Progression at other sites or death from any cause were treated as competing risks. Of note, lesions with metabolic tumor volumes (MTV) below 25 cc were treated with relatively low radiotherapy doses of 57 Gy (n=20) or 52.5 Gy (n=72).

#### 4.4 Activity Monitoring

In addition to pioneering a novel way to deliver thoracic radiotherapy, we at the Montefiore/Einstein Cancer Center have established a novel program to monitor patients for acute complications during radiotherapy. We performed a pilot trial in which patients undergoing concurrent chemoradiotherapy for a variety of malignancies were equipped with commercial fitness trackers, and activity levels were monitored throughout the treatment course[34]. We found that daily step counts can serve as powerful and dynamic predictors of unplanned hospitalization during chemoradiotherapy. Specifically, we found a 38% reduction in the risk of hospitalization for every 1,000 steps taken each day. In a follow-up study, we are utilizing activity data to provide customized supportive care for patients based on changes in activity levels, with the aim of reducing the rate of hospitalization during treatment. A third trial at our institution is testing a simple pedometer-based walking program as an intervention to reduce systemic inflammation and reduce treatment interruptions during chemoradiotherapy. A fourth study will explore activity data as a predictor of adverse events for patients with advanced malignancies receiving systemic therapy. Activity data is now collected automatically by wireless access clients every time a patient enters our cancer center.

#### 4.5 Patient-Reported Outcomes

Patient-reported outcomes are becoming a standard tool for evaluating health-related quality of life, treatment preferences, and treatment quality in cancer care[35]. They may be particularly important in studies involving radiotherapy for NSCLC. This is exemplified by the results of RTOG 0617, which was a multi-institutional randomized trial testing uniform radiotherapy dose escalation (including all tumors and regional lymph nodes) with concurrent chemotherapy for LA-NSCLC. Dose escalation from 60 Gy to 74 Gy was unexpectedly found to increase the risk of mortality, with median overall survival durations of 29 months with the standard dose of 60 Gy and only 20 months for subjects treated with 74 Gy[17]. Investigators found no statistically significant differences in serious (grade  $\geq 3$ ) adverse events between radiotherapy dose groups, demonstrating the disconnect between physician-scored toxicity and important clinical outcomes. Impairments in patient-reported quality of life, on the other hand, occurred more frequently in the high dose radiotherapy arm[36]. Additionally, baseline quality of life score was found to be a powerful predictor of overall survival.

The National Cancer Institute recently developed the Patient-Reported Outcomes Version of the Common Terminology Criteria for Adverse Events (PRO-CTCAE)[37]. The PRO-CTCAE item library is comprised of 78 symptomatic adverse events, each of which is elicited using between one and three questions (representing frequency, severity, and/or interference), for a total of 124 individual questions. For any given clinical trial, relevant PRO-CTCAE items can be selected from the online library to create a concise patient questionnaire that has been validated in several languages. This promising tool has not yet been utilized extensively in chemoradiotherapy trials for NSCLC. One recent study demonstrated the extent to which CTCAE and PRO-CTCAE findings may differ in this setting[38]. As an example, clinicians using CTCAE reported that high-level anxiety occurred in 0/130 subjects. PRO-CTCAE demonstrated that 28/120 subjects

had high-level anxiety. Large differences between CTCAE and PRO-CTCAE were observed for several other adverse events, including anorexia, cough, dysphagia, fatigue, and pain.

[figure not shown]
We have developed a concise PRO-CTCAE tool that includes the elements that are likely most relevant to LA-NSCLC patients who are treated with thoracic radiotherapy (Appendix). We expect that patient-reported outcomes for these elements will be improved with the use of radiotherapy and pembrolizumab compared to standard chemoradiotherapy in this setting.

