**Hypothesis:** We hypothesize that sequential pembrolizumab and radiotherapy for locally advanced NSCLC not significantly increase rates of pneumonitis compared to standard concurrent chemoradiotherapy.

(7) **Objective:** To demonstrate, within the limitations of a nonrandomized study, that sequential pembrolizumab and radiotherapy for locally advanced NSCLC reduces patient-reported treatment-related toxicities compared to standard concurrent chemoradiotherapy.

**Hypothesis:** We hypothesize that sequential pembrolizumab and radiotherapy for locally advanced NSCLC reduces patient-reported treatment-related toxicities compared to standard concurrent chemoradiotherapy.

(8) **Objective:** To demonstrate, within the limitations of a nonrandomized study, that sequential pembrolizumab and radiotherapy for locally advanced NSCLC preserves physical function compared to standard concurrent chemoradiotherapy.

**Hypothesis:** We hypothesize that sequential pembrolizumab and radiotherapy for locally advanced NSCLC preserves physical function, as measured by daily step counts, compared to standard concurrent chemoradiotherapy.

(9) **Objective:** To demonstrate, within the limitations of a nonrandomized study, that sequential pembrolizumab and radiotherapy for locally advanced NSCLC reduces hospitalization rates compared to standard concurrent chemoradiotherapy.

**Hypothesis:** We hypothesize that sequential pembrolizumab and radiotherapy for locally advanced NSCLC reduces hospitalization rates compared to standard concurrent chemoradiotherapy.

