**Table 3 Dose modification and toxicity management guidelines for immune-related AEs associated with pembrolizumab**

General instructions:				
Immune-related AEs	Toxicity grade or conditions (CTCAEv4.0)	Action taken to pembrolizumab	irAE management with corticosteroid and/or other therapies	Monitor and follow-up
Pneumonitis	Grade 2	Withhold	
 
Administer corticosteroids (initial dose of 1-2 mg/kg prednisone or equivalent) followed by taper
 
	
 
Monitor participants for signs and symptoms of pneumonitis
 
Evaluate participants with suspected pneumonitis with radiographic imaging and initiate corticosteroid treatment
 
Add prophylactic antibiotics for opportunistic infections
 

	Grade 3 or 4, or recurrent Grade 2	Permanently discontinue		
Diarrhea / Colitis	Grade 2 or 3	Withhold	
 
Administer corticosteroids (initial dose of 1-2 mg/kg prednisone or equivalent) followed by taper
 
	
 
Monitor participants for signs and symptoms of enterocolitis (ie, diarrhea, abdominal pain, blood or mucus in stool with or without fever) and of bowel perforation (ie, peritoneal signs and ileus).
 
Participants with <math>\geq</math> Grade 2 diarrhea suspecting colitis should consider GI consultation and performing endoscopy to rule out colitis.
 
Participants with diarrhea/colitis should be advised to drink liberal quantities of clear fluids. If sufficient oral fluid intake is not feasible, fluid and electrolytes should be substituted via IV infusion.
 

	Grade 4	Permanently discontinue		

AST / ALT elevation or Increased bilirubin	Grade 2	Withhold	
 
Administer corticosteroids (initial dose of 0.5- 1 mg/kg prednisone or equivalent) followed by taper
 
	
 
Monitor with liver function tests (consider weekly or more frequently until liver enzyme value returned to baseline or is stable)
 

	Grade 3 or 4	Permanently discontinue	
 
Administer corticosteroids (initial dose of 1-2 mg/kg prednisone or equivalent) followed by taper
 
	

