## Appendix 5: PRO-CTCAE Assessment Tool

### NCI PRO-CTCAE™ ITEMS

#### Item Library Version 1.0

As individuals go through treatment for their cancer they sometimes experience different symptoms and side effects. For each question, please check or mark an  in the one box that best describes your experiences over the past 7 days...

1.	In the last 7 days, what was the SEVERITY of your DIFFICULTY SWALLOWING at its WORST?				
 None  Mild  Moderate  Severe  Very severe					

2.	In the last 7 days, what was the SEVERITY of your DECREASED APPETITE at its WORST?				
 None  Mild  Moderate  Severe  Very severe					
In the last 7 days, how much did DECREASED APPETITE INTERFERE with your usual or daily activities?					
 Not at all  A little bit  Somewhat  Quite a bit  Very much					

3.	In the last 7 days, how OFTEN did you have NAUSEA?				
 Never  Rarely  Occasionally  Frequently  Almost constantly					
In the last 7 days, what was the SEVERITY of your NAUSEA at its WORST?					
 None  Mild  Moderate  Severe  Very severe					

4.	In the last 7 days, what was the SEVERITY of your SHORTNESS OF BREATH at its WORST?				
 None  Mild  Moderate  Severe  Very severe					
In the last 7 days, how much did your SHORTNESS OF BREATH INTERFERE with your usual or daily activities?					
 Not at all  A little bit  Somewhat  Quite a bit  Very much					

5.	In the last 7 days, what was the SEVERITY of your COUGH at its WORST?				
 None  Mild  Moderate  Severe  Very severe					
In the last 7 days, how much did COUGH INTERFERE with your usual or daily activities?					

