## NCI PRO-CTCAE™ ITEMS

### Item Library Version 1.0

6. In the last 7 days, what was the SEVERITY of your WHEEZING (WHISTLING NOISE IN THE CHEST WITH BREATHING) at its WORST?

None    Mild    Moderate    Severe    Very severe

7. In the last 7 days, what was the SEVERITY of your SKIN BURNS FROM RADIATION at their WORST?

None    Mild    Moderate    Severe    Very severe    Not applicable

8. In the last 7 days, what was the SEVERITY of your DIZZINESS at its WORST?

None    Mild    Moderate    Severe    Very severe

In the last 7 days, how much did DIZZINESS INTERFERE with your usual or daily activities?

Not at all    A little bit    Somewhat    Quite a bit    Very much

9. In the last 7 days, what was the SEVERITY of your FATIGUE, TIREDNESS, OR LACK OF ENERGY at its WORST?

None    Mild    Moderate    Severe    Very severe

In the last 7 days, how much did FATIGUE, TIREDNESS, OR LACK OF ENERGY INTERFERE with your usual or daily activities?

Not at all    A little bit    Somewhat    Quite a bit    Very much

10. In the last 7 days, how OFTEN did you feel ANXIETY?

Never    Rarely    Occasionally    Frequently    Almost constantly

In the last 7 days, what was the SEVERITY of your ANXIETY at its WORST?

None    Mild    Moderate    Severe    Very severe

In the last 7 days, how much did ANXIETY INTERFERE with your usual or daily activities?

Not at all    A little bit    Somewhat    Quite a bit    Very much

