## NCI PRO-CTCAE™ ITEMS

### Item Library Version 1.0

11. In the last 7 days, how OFTEN did you FEEL THAT NOTHING COULD CHEER YOU UP?				
 Never  Rarely  Occasionally  Frequently  Almost constantly				
In the last 7 days, what was the SEVERITY of your FEELINGS THAT NOTHING COULD CHEER YOU UP at their WORST?				
 None  Mild  Moderate  Severe  Very severe				
In the last 7 days, how much did FEELING THAT NOTHING COULD CHEER YOU UP INTERFERE with your usual or daily activities?				
 Not at all  A little bit  Somewhat  Quite a bit  Very much				
12. In the last 7 days, how OFTEN did you have SAD OR UNHAPPY FEELINGS?				
 Never  Rarely  Occasionally  Frequently  Almost constantly				
In the last 7 days, what was the SEVERITY of your SAD OR UNHAPPY FEELINGS at their WORST?				
 None  Mild  Moderate  Severe  Very severe				
In the last 7 days, how much did SAD OR UNHAPPY FEELINGS INTERFERE with your usual or daily activities?				
 Not at all  A little bit  Somewhat  Quite a bit  Very much				

Do you have any other symptoms that you wish to report?

 Yes	 No
---------------------------	--------------------------

Please list any other symptoms:

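### Objective 7 claims less patient-reported toxicity in general, but the PRO-CTCAE tool was chosen for thoracic radiotherapy and asks about none of the bowel symptoms that Table 3 ties to pembrolizumab

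*Combined protocol and SAP*

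**What the plan says.** - **The claim.** Objective and hypothesis 7 (Section 3.2) state that sequential pembrolizumab and radiotherapy "reduces patient-reported treatment-related toxicities compared to standard concurrent chemoradiotherapy". The matching safety endpoint in Section 4.6.2.2 is equally general and is scored with PRO-CTCAE.
- **The instrument.** The stated selection basis in Section 4.5 is: "We have developed a concise PRO-CTCAE tool that includes the elements that are likely most relevant to LA-NSCLC patients who are treated with thoracic radiotherapy". Pembrolizumab toxicity is not named as a criterion. The protocol then says: "We expect that patient-reported outcomes for these elements will be improved with the use of radiotherapy and pembrolizumab".
- **The known drug toxicity.** Table 3 (Section 5.2.1.2), in its diarrhea/colitis row, instructs sites: "Monitor participants for signs and symptoms of enterocolitis (ie, diarrhea, abdominal pain, blood or mucus in stool with or without fever".
- **The catch-all.** After its symptom items, Appendix 5 asks "Do you have any other symptoms that you wish to report", answered yes or no and followed by space for a list.
- **The analysis.** Section 8.2 reports PRO-CTCAE adverse event rates as counts with percentages and compares the cohorts with chi-square or Fisher tests, labelled exploratory. It defines no score, no key item and no handling of write-in symptoms.

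**The concern.** The objective covers patient-reported treatment toxicity without limit, while the instrument was selected for one component of treatment, thoracic radiotherapy, which both cohorts receive. What differs between the cohorts is mainly the systemic treatment. Section 5.5 plans up to 15 pembrolizumab doses over about a year for PembroRT. Section 5.2.2 gives ChemoRT weekly carboplatin and paclitaxel, with immunotherapy only as an optional adjuvant.

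A toxicity that the protocol itself links to pembrolizumab is not prompted for on the form used to claim better tolerability. If PembroRT shows a lower rate on the 12 items, the plan as written would let that be reported as less patient-reported treatment toxicity overall, although bowel symptoms were never asked about.

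**Working it through.** The point concerns instrument content. No sample size, power or alpha figure in the plan depends on it, so there is no stated figure to reproduce.

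**Step 1: count the items (Appendix 5).** Questions per symptom: swallowing 1, appetite 2, nausea 2, shortness of breath 2, cough 2, wheezing 1, radiation skin burns 1, dizziness 2, fatigue 2, anxiety 3, inability to be cheered up 3, sadness 3.

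Total: 12 symptoms; 1+2+2+2+2+1+1+2+2+3+3+3 = 24 questions.

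**Step 2: match against Table 3.** The bowel symptoms named there are diarrhea, abdominal pain, blood in stool and mucus in stool. Matches in Appendix 5: 0 of 4. The nearest gastrointestinal items are appetite and nausea. By contrast, typical radiotherapy effects have their own items: "SEVERITY of your DIFFICULTY SWALLOWING at its WORST" and "SEVERITY of your SKIN BURNS FROM RADIATION at their WORST".

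**Step 3: compare exposure.** All 25 PembroRT subjects are planned for pembrolizumab. Of about 38 ChemoRT subjects, an unstated number may receive adjuvant immunotherapy. The omission is therefore not neutral by design, although its net effect is open.

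**Step 4: illustrate the size. All rates here are assumed; none is in the documents.** Suppose the endpoint is any PRO-CTCAE symptom above some threshold. Let the listed items give rate q in both cohorts. Let bowel symptoms occur independently at rate b1 in PembroRT and b2 in ChemoRT.

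With bowel items added, a cohort's rate is 1 - (1-q)(1-b) = q + (1-q)b. The PembroRT-minus-ChemoRT difference therefore changes by (1-q)(b1-b2).

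| b1 vs b2 | q = 30% | q = 60% |
|---|---|---|
| 5% vs 0% | 0.7 × 5 = 3.5 points | 0.4 × 5 = 2 points |
| 10% vs 5% | 3.5 | 2 |
| 20% vs 5% | 10.5 | 6 |
| 20% vs 0% | 14 | 8 |
| 10% vs 10% | 0 | 0 |
| 5% vs 10% | -3.5 | -2 |

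Where PembroRT has the higher bowel rate, the present form hides 2 to 14 points that would count against it. With equal rates it hides nothing, and with a higher ChemoRT rate the sign reverses. The same formula applied to an omitted chemotherapy symptom, for which b2 would exceed b1, also gives a negative shift.

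**The case against.** The strongest case on the other side has several parts.

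- **The direction is not proved.** A reader might infer that the comparison is tilted towards PembroRT. The documents do not establish that. They give no bowel symptom rate for either cohort. Section 5.2.2 allows adjuvant immunotherapy in ChemoRT, and Section 4.6 describes a year of adjuvant durvalumab as part of a changed standard of care. Symptoms specific to chemotherapy may be missing as well. This stands: there is a risk of under-counting on one side, and the net bias is unknown.
- **The tool is not blind to pembrolizumab.** A reader might infer that the drug's toxicity cannot register at all. That is wrong. Shortness of breath, cough and wheezing would pick up pneumonitis symptoms, and appetite, nausea, fatigue and dizziness are general. A patient with colitis might already be counted through one of these. This stands.
- **Clinicians capture bowel events.** CTCAE grading covers them for objective 5, so the gap is confined to objective 7. It would be tempting to answer that Section 4.5 shows clinician grading missing such symptoms. Its examples are anxiety, anorexia, cough, dysphagia, fatigue and pain, and no bowel symptom is among them.
- **The open question helps.** It does, and nothing in Section 8.2 excludes write-in answers. But they are unprompted, carry no severity grade and have no coding rule, so the gap is softened rather than closed.
- **Skin.** One might extend the point to non-radiation skin symptoms. Table 3 has no skin row, and skin is mentioned only under possible work-up (Sections 5.2.1.2 and 5.4.3). That is too thin to press.
- **Scope is disclosed and hedged.** Section 4.5 states the selection basis, objective 7 acknowledges the nonrandomized design, and Section 8.2 calls the comparisons exploratory. This lowers the stakes. It does not bring the wording of objective 7 into line with what the form asks, because the hedge concerns allocation and not instrument content.

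**Conclusion.** The concern holds as a mismatch between claim and instrument. Objective 7 speaks of patient-reported treatment toxicity in general, while the 12-symptom form was selected for thoracic radiotherapy and covers 0 of the 4 bowel symptoms named in Table 3. Because pembrolizumab is planned for every PembroRT subject and immunotherapy is optional in ChemoRT, the omission risks under-counting PembroRT toxicity.

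Neither the size nor the net direction can be derived from the documents. The range of -3.5 to +14 points rests on assumed bowel rates (5-20% in PembroRT, 0-10% in ChemoRT), a common rate of 30-60% on the other items, and independence. It shows only that the effect could matter in cohorts of 25 and about 38. The primary endpoint and its power are untouched. This is a cheap improvement.

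**What to change.** **Preferred.** In both cohorts and at the PRO-CTCAE assessments already in the flow chart, add library items for diarrhea and abdominal pain. Add the corresponding items for chemotherapy-specific symptoms, so that the form does not lean the other way. The protocol puts the library at 78 symptoms but does not list them, so confirm the exact items there. In Section 8.2, state how answers to the open question are coded and whether they enter the compared rates.

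**Fallback if the form cannot change.** Restate objective and hypothesis 7 as a comparison of the 12 listed symptoms, and state in the protocol and the report that bowel symptoms were not elicited.

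**Cost.** The preferred change makes the form slightly longer, and the new items would exist only for later assessments, so patients assessed before the change would lack them. The fallback costs only a narrower claim. Neither needs an extra visit.

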#### 4.6 Study Rationale

We hypothesize that a combination of pembrolizumab and dose-painted radiotherapy will yield improved efficacy and tolerability compared to standard chemoradiotherapy for locally advanced NSCLC patients with high ( $\geq 50\%$ ) PD-L1 expression. We will explore this hypothesis in the “pembroRT” arm of this prospective non-randomized trial. Subjects with PD-L1 expression below 50% will also be enrolled to a “chemoRT arm” and treated with standard concurrent chemoradiotherapy, to allow exploratory comparisons of toxicities and clinical outcomes following pembrolizumab and radiotherapy versus chemotherapy and radiotherapy. Subjects on both arms will use wearable fitness trackers, which will allow us to monitor closely for adverse events and demonstrate that our novel treatment approach preserves functional status compared to standard chemoradiotherapy. We will also follow patient-reported outcomes for subjects in both cohorts.

While study subjects allocated to the “chemoRT” arm of this trial based on low PD-L1 expression, will not be receiving novel therapy, we believe that the inclusion of the “chemoRT” arm in this trial is critical for several reasons:

- *To characterize outcomes following chemoradiotherapy and modern adjuvant therapy.* Since RTOG 0617 was conducted (2007-2011)[17], and even after our in-house PAINT trial (2013-2016)[33], early results from the PACIFIC trial have changed the standard of care for many patients with locally advanced NSCLC[10]. Clinicians caring for this patient population are currently in an unusual situation, where we consider treatment with one year of adjuvant durvalumab following chemoradiotherapy without published data demonstrating how this treatment affects overall survival. It is therefore important that we characterize survival rates in a contemporary patient cohort receiving chemoradiotherapy for locally advanced NSCLC. Of note, the PACIFIC trial demonstrated that the prolongation of PFS and distant metastasis-free survival with durvalumab was not influenced by PD-L1 expression. Additionally, we have not found that PD-L1 expression is a prognostic factor for patients treated with chemoradiotherapy at our institution (see figures below). While comparisons of outcomes in our two study cohorts will be limited by the non-randomized treatment allocation, outcomes in the “chemoRT” cohort will provide some frame of reference for outcomes seen in the “pembroRT” group.

Kaplan-Meier curves depicting progression-free survival and overall survival in patients who have been treated with concurrent chemoradiotherapy for locally advanced NSCLC at our institution and underwent tumor PD-L1 testing.

- To allow comparison of the safety profiles of “pembroRT” and “chemoRT”. We expect that, compared to standard chemoradiotherapy, sequential pembrolizumab and dose-painted accelerated radiotherapy will reduce clinician and patient-reported serious adverse event rates, reduce hospitalization rates, and preserve physical function. Of note, we have not found that PD-L1 expression is associated with hospitalization rates or step counts in patients we have treated with chemoradiotherapy for locally advanced NSCLC (see figures below). While comparisons of outcomes in our two study cohorts will be limited by the non-randomized treatment allocation, adverse event rates in the “chemoRT” cohort will provide some frame of reference for those seen in the “pembroRT” group.

